Study Protocol

Intravenous Iron for Iron-Deficiency Anemia in Pregnancy: A Randomized Controlled Trial (IVIDA)

PI: [name]; Indiana University

Version 6.2

NCT03438227

SYNOPSIS

Objective: To assess the effectiveness and safety of treating iron-deficiency anemia in pregnant women with intravenous iron compared to oral iron.

Background: Iron deficiency is the most common cause of anemia in pregnancy worldwide, and, when severe, can have serious consequences for mothers and babies. In the U.S., anemia affects nearly 20% of pregnancies, and the majority are iron-deficiency anemia. While treatment of iron-deficiency anemia with iron supplementation is recommended, treatment strategies remain controversial. The American College of Obstetrics and Gynecology (ACOG) recommends oral iron supplementation for iron-deficiency anemia in pregnancy and postpartum, with intravenous iron reserved for the rare patient who cannot tolerate or will not take oral iron. Conversely, UK professional organizations recommend a more liberal use of intravenous iron for the treatment of iron-deficiency anemia in pregnancy and postpartum. The reason for these disparate recommendations is that few high-quality studies comparing oral to intravenous iron have been conducted in developed countries, and the potential impact of intravenous iron treatment on obstetric and perinatal outcomes remains unclear. The most recent Cochrane review—mostly of trials conducted in low-income countries—found that, although intravenous iron more effectively improved hemoglobin levels and iron stores compared to oral iron, no clinical outcomes were assessed and there were insufficient data on adverse effects. Thus, there is a need for a well-designed trial to clarify whether intravenous iron should be used more liberally for the treatment of iron-deficiency anemia in pregnancy in the U.S.

Study design: Open-label, randomized controlled trial

Primary outcome: Maternal anemia (hemoglobin (Hgb) <11mg/dl) on admission for labor & delivery

Secondary outcomes:

- 1. Safety (infusion reactions)
- 2. Maternal outcomes (Hgb, serum ferritin, blood transfusion, mode of delivery)
- 3. Neonatal outcomes (gestational age at delivery, infant birth weight, cord gases, umbilical artery lactate, APGAR scores, cord blood Hgb & ferritin, neonatal morbidities, postpartum disposition)

Subject selection:

Inclusion criteria

- Pregnant women
- 18 years or older
- Diagnosed with iron-deficiency anemia

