Iron deficiency is the most common cause of anemia in pregnancy worldwide, and, when severe, can have serious consequences for mothers and babies. In the U.S., anemia affects nearly 20% of pregnancies and the majority are iron-deficiency anemia. Patients on oral iron for iron-deficiency anemia with a Hgb<11mg/dl at the time of delivery have a 3-fold increased risk of peripartum blood transfusion (3.8% vs 1.3%, RR 2.90, 95% CI 1.97, 4.36) based on institutional data from Washington University in St. Louis. Therefore, treatment of iron-deficiency anemia with iron supplementation is recommended. However, there is controversy about the treatment strategies.

The American College of Obstetrics and Gynecology recommends oral iron supplementation for iron-deficiency anemia in pregnancy, with intravenous iron reserved only for the "rare patient who cannot tolerate or will not take oral iron." Conversely, guidelines from the U.K. are more liberal on the use of intravenous iron for the treatment of iron-deficiency anemia in pregnancy. Both treatment guidelines are based on limited data regarding the risks and benefits of intravenous iron for treatment of iron-deficiency anemia in pregnancy. The majority of randomized trials were conducted in developing country settings. In fact, few high-quality studies have been conducted in developed countries, and none has been conducted in the U.S. Moreover, there is limited data from prior studies on the impact of intravenous iron treatment on perinatal outcomes. The most recent Cochrane review including mostly trials conducted in low-income countries found that, although intravenous iron improved hemoglobin levels and iron stores more than the oral route, no clinical outcomes were assessed and there were insufficient data on adverse effects. The authors concluded that "large, good quality trials, assessing clinical outcomes including adverse effects ... are required."

OBJECTIVE

This study aims to assess the effectiveness and safety of treating pregnant women with iron-deficiency anemia with a protocol including intravenous iron compared with a protocol based on oral iron. We *hypothesize* that treating iron-deficiency anemia with intravenous iron is associated with improved maternal and neonatal outcomes compared with treatment using oral iron.

STUDY DESIGN AND METHODS

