Overview: We will conduct an open-label, randomized controlled trial to assess the effectiveness and safety of treating iron-deficiency anemia in pregnant women with intravenous iron compared with oral iron. We test the *hypothesis* that treating iron-deficiency anemia with intravenous iron is associated with improved maternal and neonatal outcomes compared with oral iron. We will use broad inclusion criteria and analyze data using the intention-to-treat principle to increase generalizability of the findings.

Inclusion & exclusion criteria:

Inclusion criteria:

- Pregnant women
- 18 years or older
- Diagnosed with iron-deficiency anemia
 - Serum ferritin <30ug
 - o Hgb <10 g/dl
- Between 24 34 weeks gestation
- Plan to deliver at an in-network hospital
- Able and willing to give informed consent

Exclusion criteria:

- Diagnosis of non-iron-deficiency anemia
- Multiple gestation
- Known or suspected major fetal anomaly or aneuploidy
- Planned delivery at out-of-network hospital
- Unable or unwilling to give consent

Study outcomes:

Primary outcome: The primary outcome of the trial is maternal anemia, defined as Hgb <11mg/dl, on admission for labor and delivery.

Secondary outcomes:

- 1. Safety:
 - i. Mild/moderate infusion reactions: chest tightness, itching, urticaria, flushing, nausea/vomiting, arthralgia, back or joint aches, mild shortness of breath, tachycardia, hypertension or hypotension, abdominal pain, diarrhea, peripheral edema, headache, dizziness, syncope, or numbness.
 - ii. Major infusion reaction: anaphylaxis-like reaction, seizures, or non-reassuring fetal heart rate tracing.

2. Maternal outcomes:

- i. Hgb at admission to labor and delivery
- ii. Hgb on postpartum day 1
- iii. Ferritin at admission to labor and delivery
- iv. blood transfusion
- v. mode of delivery
- vi. postpartum disposition
- vii. readmission

3. Neonatal outcomes

- i. gestational age at delivery
- ii. birth weight
- iii. cord gases (if performed as SOC)
- iv. umbilical artery lactate (if performed as SOC)
- v. APGAR scores
- vi. Hgb (obtained from cord blood)
- vii. Ferritin (obtained from cord blood)
- viii. neonatal morbidities
- ix. postpartum disposition

Screening:

[figure not shown]

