reactions. This amounts to a cumulative dose of 1000mg IV iron dextran. If iron dextran is unavailable due to drug shortage, ferumoxytol will be substituted for this treatment group. Subjects will be given an initial 510mg IV dose in 100 ml 0.9% sodium chloride over at least 15 minutes. This dose will be followed by a second dose of the same concentration 3 to 8 days later. All iron infusions will occur on an obstetric unit equipped with continuous monitoring and emergency equipment. Patients will have continuous fetal monitoring throughout and at least 30 minutes after the infusion. Patients will be called by research staff 48 - 72 hours after infusion (second infusion if administering ferumoxytol) to assess for transfusion reactions. Women who receive intravenous iron will not receive further oral iron supplementation during pregnancy. Postpartum iron supplementation will be left to provider discretion.

Figure 1: Study protocol

^{*}If iron dextran is unavailable due to drug shortage, ferumoxytol will be substituted. The initial dose will be 510mg ferumoxytol IV followed by a second dose of 510mg ferumoxytol IV 3 to 8 days later.

STUDY PROCEDURES

Study patients will have hemoglobin drawn at admission to labor and delivery and on postpartum day one. Neonatal hemoglobin and ferritin (and blood gases and/or lactate if performed out of clinical necessity) will be assessed via cord blood. Obstetric and neonatal outcomes will be collected by a trained research nurse. Subjects randomized to the oral iron group will be asked to report compliance with taking oral iron supplements as well as any side effects of taking the oral iron. This self-report will be assessed during their admission to labor and delivery (or via phone up to 2 days after discharge). See **Figure 2** for schedule of events. Pregnancy, labor and delivery management will be per standard obstetric practice.

Figure 2: Schedule of events

Event	Screening & Enrollment 24-34 weeks	Prenatal Period	48-72 hrs after infusion*	Delivery	Postpartum period prior to discharge
Inclusion/Exclusion	Х				
Informed Consent	X				
Demographics	X				
Prenatal history	X				
Randomization to oral iron vs. IV iron	Х	Oral continues Infusion occurs*			
Phone call: AEs/ outcomes of IV iron			Х		
Effects & outcomes of oral iron supplementation (self-report)		X (Once 2-4 weeks after randomization)		х	
Oral iron compliance (self-report)				х	
Maternal blood draw: Hgb	SOC			х	X PPD1

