Maternal blood draw: Serum ferritin	SOC			х	
Cord blood collection & processing (Hgb & ferritin; cord gas and/or lactate if performed as clinical necessity)				Х	
Delivery & neonatal outcomes via chart abstraction					Х

^{*}If ferumoxytol is administered due to shortage of iron dextran, two infusions will occur in the prenatal period as outlined in the randomization section of this document. The post-infusion phone call will occur 48-72 hours after the second infusion.

Data analysis: Analyses will follow the intention to treat principle, in which patients will be analyzed in the group to which they were randomized whether or not they received the assigned treatment. Continuous variables will be compared using the Student's t-test or Mann Whitney t test, as appropriate. Categorical variables will be compared using the t or Fisher's exact test, as appropriate. We will calculate crude and unadjusted risk estimates and differences. We will use multivariable logistic regression to adjust for potential confounders. We will estimate the number needed to treat to prevent occurrence of one primary outcome.

Sample size estimation: Based on institutional data the baseline rate of anemia (Hgb<11mg/dl) on admission to labor and delivery among women on supplemental oral iron is 38.5%. We estimate that 108 patients will provide 80% power to detect a 60% or greater relative difference in anemia (38.5% versus ≤15.4%) with intravenous iron (alpha=0.05, 2-tailed test). We will recruit **120 patients** to account for an anticipated 10% loss to follow-up (**Table 1**).

The anticipated effect size of 60% is plausible and conservative. A study by Al *et al.*, the only study that reported the outcome of Hgb <11 at the time of delivery, showed an effect size of 88% (4.4% versus 37.8%, RR 0.12, 95% CI 0.03, 0.48).⁴ Based on preliminary data showing that 10 pregnant women received intravenous iron in 6 weeks at the Washington University Medical Center, we anticipate that the 124 patients will be recruited within 15 months.

Table 1: Sample size estimation (Baseline: 38.5%, Power: 80%, alpha 0.05, loss: 10%)				
Risk Estimate RR (%)	Anticipated Rate	N	N+10%	
0.67 (33)	25.8%	418	460	
0.60 (40)	23.1%	276	304	
0.50 (50)	19.3%	168	185	
0.40 (60)	15.4%	108	120	
0.33 (67)	12.7%	82	90	
0.30 (70)	11.6%	74	81	

HUMAN SUBJECTS PROTECTION

Assessment of Risks

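### Intention to treat is the only analysis-group rule, so as written it also governs infusion reactions and would understate the risk per infused woman if any IV-arm woman is not infused

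*Combined protocol and SAP*

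**What the plan says.** The Data analysis paragraph (under Study Procedures) applies intention to treat to the trial's analyses, so that "patients will be analyzed in the group to which they were randomized whether or not they received the assigned treatment". It makes no exception for safety outcomes. The Overview under Study Design and Methods repeats the rule for the trial's data in general: "analyze data using the intention-to-treat principle to increase generalizability of the findings".

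Safety is part of the stated aim. The Objective section reads "This study aims to assess the effectiveness and safety of treating pregnant women with iron-deficiency anemia", and infusion reactions come first among the secondary outcomes in both the Synopsis and the Study outcomes section. The severe category is defined as "Major infusion reaction: anaphylaxis-like reaction, seizures, or non-reassuring fetal heart rate tracing".

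The section on Randomization and Treatment Groups adds a second product: "If iron dextran is unavailable due to drug shortage, ferumoxytol will be substituted for this treatment group". Iron dextran is given as a test dose plus one infusion, ferumoxytol as two infusions.

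The documents contain no safety population, no grouping by treatment received and no infused-only denominator.

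**The concern.** An infusion reaction requires an infusion. A woman randomized to IV iron who withdraws, declines or delivers before infusion cannot contribute a reaction, yet the grouping rule keeps her in the IV arm. Figure 2 places infusion in the prenatal period, after enrollment, so there is an interval in which this can happen. The rule itself foresees women who do not receive their assigned treatment.

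The mirror case is an oral-arm woman who is given IV iron. The protocol has no rule for this, but pregnancy care follows standard practice, and the Background notes that US guidance allows IV iron for women who cannot tolerate or will not take the oral form. Under the stated rule, any reaction she has goes into the oral column.

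For a superiority comparison of efficacy, dilution of this kind is conservative. For harm it works the other way and makes IV iron look safer per infusion than it is. The Synopsis gives insufficient adverse-effect data as one reason for the trial, so the denominator should be fixed before results are seen.

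**Working it through.** **What the plan supplies.** It gives 120 women randomized 1:1, so 60 per arm. That total reproduces. With 38.5% versus 15.4%, two-sided alpha 0.05, 80% power and unpooled variance, the sample-size formula gives 53.99, so 54 per arm and 108 in total; 108/0.9 = 120. The plan states no reaction rate, non-infusion rate or crossover rate, so there is no safety figure to reproduce.

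**Assumed quantities.**
- r: reaction risk per infused woman, taken as equal in both arms
- u: fraction of the IV arm never infused
- c: fraction of the oral arm given IV iron
- never-infused women count in the denominator without an event

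**Expected rates under the rule as written.**
- IV arm: r(1-u)
- Oral arm: r × c
- Difference: r(1-u-c)

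Among women actually infused, the expected rate is r. If u = c = 0, the two approaches agree.

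**Non-infusion only (c = 0).**

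| u | r = 20% | r = 5% |
|---|---|---|
| 5% | 0.20 × 0.95 = 19% | 0.05 × 0.95 = 4.75% |
| 10% | 0.20 × 0.90 = 18% | 0.05 × 0.90 = 4.5% |
| 15% | 0.20 × 0.85 = 17% | 0.05 × 0.85 = 4.25% |

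**Both departures together.** With r = 20% and u = c = 10%, the IV arm shows 18% and the oral arm 2%. The difference is 16 points instead of 20, a shrinkage of u + c = 20%.

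**No major reaction observed.** The exact (Clopper-Pearson) two-sided 95% upper limit with zero events in n women is 1 - 0.025^(1/n).
- 60 randomized: 1 - 0.025^(1/60) = 5.96%
- 54 infused (u = 10%): 1 - 0.025^(1/54) = 6.60%

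The one-sided 95% bounds, 1 - 0.05^(1/n), are 4.9% and 5.4%. The 54 here is 60 less an assumed 10% not infused. That it equals the evaluable number per arm in the sample-size section is coincidence.

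**Does other text set the denominator?** Several safety provisions are tied to exposure: nurse monitoring during infusion, the call 48-72 hours afterwards, the limits of some events of special interest to the infusion timeframe, and an adverse-event definition that refers to a subject given the product. All of these govern what is collected and reported. None says in which group, or over which denominator, reactions are analyzed.

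**The case against.** The strongest objection is that the randomized-arm rate is not wrong in itself. The Objective compares a protocol including IV iron with one based on oral iron, and for the harm of being assigned to a protocol, r(1-u) is the right quantity. This stands, and it is why the randomized-arm table should be kept. It does not supply the risk of an infusion, which is what an outcome named "Safety (infusion reactions)" naturally suggests and which the plan does not specify.

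Second, the grouping sentence does not say that a woman who was never infused is coded as having no reaction; she could be treated as missing. That is fair, but the plan does not say so either, and the literal reading leaves her in the denominator.

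Third, the shifts are small. At r = 20% they are 1 to 3 points, against a standard error of sqrt(0.2 × 0.8/60), about 5 points. At r = 5% they are 0.25 to 0.75 points. The risk section calls most of these symptoms less common and the major ones rare. All of this stands.

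Fourth, a reader might infer that a tenth of infused women would be reported in the wrong arm. The documents do not support that. It needs 10% non-infusion and 10% crossover together, both assumed, and it counts women rather than reactions: 60 × 0.10 × 0.20 = 1.2 reactions expected. The protocol provides for no crossover, each event gets a relationship-to-drug assessment, and a reaction labelled as an infusion reaction is unlikely to be read as oral-iron toxicity.

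Fifth, a reader might infer that the intention-to-treat rule causes the two IV products to be pooled. It does not. Pooling would persist in an as-treated set unless the plan asked for a split, and ferumoxytol is used only in a shortage.

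**Conclusion.** The gap is real and modest. The plan's only grouping rule extends to an outcome that only infused women can have, and nothing elsewhere sets another denominator. Whenever u is above zero, the expected IV-arm rate falls below the risk per infused woman. Whenever c is above zero, some reactions move to the oral column. Neither departure can push the IV-arm figure above the risk per infusion.

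The size rests wholly on assumed rates: 20% becomes 19-17% for 5-15% not infused, and the zero-event upper limit is 6.0% rather than 6.6% at 10% not infused. If every IV-arm woman is infused and no oral-arm woman is, nothing changes.

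A reader might go further and infer that reaction rates will be biased, or that intention to treat is unsuitable for this trial. The documents support neither. They give no sign of how often women will go uninfused or cross over, and intention to treat is appropriate for the primary outcome. The point does not touch the sample size or the primary analysis. It should be corrected, but the trial does not depend on it.

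**What to change.** In the Data analysis paragraph, limit the intention-to-treat sentence to efficacy and perinatal outcomes. Then add wording such as: *Infusion reactions will be analyzed primarily in all women who received any intravenous iron, including the test dose, and reported as a proportion of women infused with an exact 95% confidence interval. A tabulation by randomized arm will be given as a supplementary comparison of the two treatment protocols. If ferumoxytol is used, reactions will also be listed descriptively by product received.*

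Two checks go with this. The eCRF is not shown in the documents, so confirm that it captures any IV iron given in either arm and the product used. The list of events of special interest also includes oral-iron effects such as bowel changes. The wording above does not cover them, so their grouping should be stated too.

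The cost is one paragraph of analysis text. Sample size, alpha and treatment are unchanged. The reported reaction rate may be slightly higher and its interval slightly wider, and any by-product listing may rest on few women.

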 - Serum ferritin <30ug
 - o Hgb <10 g/dl
- Between 24 34 weeks gestation
- Plan to deliver at an in-network hospital
- Able and willing to give informed consent

Exclusion criteria

- Diagnosis of non-iron-deficiency anemia
- Multiple gestation
- Known or suspected major fetal anomalies or aneuploidy
- Planned delivery at out-of-network hospital
- Unable or unwilling to give consent

Randomization and treatment: Patients who meet all inclusion criteria and no exclusion criteria will be enrolled and randomized in a 1:1 ratio using a computer-generated randomization sequence to one of two treatment protocols:

- 1. Oral Iron Supplement- Oral iron supplementation (ferrous sulfate 325mg once daily to three times daily through delivery)
- 2. Intravenous Iron- Intravenous iron infusion (1000mg of intravenous iron dextran; given as a single dose after enrollment as close as possible to 24 weeks gestation). If iron dextran is unavailable due to drug shortage, ferumoxytol will be substituted; 510 mg IV will be administered followed by a second dose (510 mg IV) 3 to 8 days after the initial dose.

Procedures: All patients presenting for prenatal care will have workup for anemia with repeat CBC at 24 to 28 weeks gestation per standard of care. Patients found to have iron-deficiency anemia (Hgb <10 g/dL and ferritin <30ug) at 24 – 28 weeks and who meet all other inclusion and exclusion parameters will be eligible to be approached for the study. In addition, patients who do not receive standard anemia screening but are diagnosed at 28 – 34 weeks gestation with iron-deficiency anemia (hemoglobin<10mg/dl and ferritin <30ug) will be eligible for the study. Subjects will be randomized to one of the two treatment groups (oral or intravenous iron supplementation). Study patients will have Hgb and ferritin drawn at delivery. Their neonates will have Hgb and ferritin drawn via cord blood at delivery. If a cord gas or umbilical artery lactate level is drawn out of clinical necessity, this data will be collected also. Chart abstraction will be used to assess additional maternal and neonatal outcomes. Pregnancy, labor and delivery management will be per standard obstetric practice.

Sample Size: 120 subjects over an estimated 15 - 18 months.

BACKGROUND

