Pregnant women attending prenatal care will be screened for anemia with repeat CBC at 24 to 28 weeks gestation per standard of care. If the initial Hgb at this gestational age is less than 10 mg/dL, they will undergo testing for iron-deficiency anemia. Iron-deficiency anemia will be defined as anemia with serum ferritin <30ug. Any pregnant woman diagnosed with iron-deficiency anemia who meets all inclusion criteria and no exclusion criteria will be eligible for the study (**Figure 1**). In addition, patients who present for prenatal care after 28 weeks gestation who meet all inclusion criteria and no exclusion criteria will be eligible for enrollment if they are diagnosed with iron-deficiency anemia prior to 34 weeks.

Randomization and Treatment Groups: Patients meeting all inclusion criteria and no exclusion criteria who sign informed consent will be enrolled and randomly assigned in a 1:1 ratio using a computer-generated randomization sequence to one of two treatment protocols. The two treatment protocols are:

- 1. Oral Iron Supplement- Oral iron supplementation will occur throughout pregnancy with ferrous sulfate at a dose range of 325mg daily to 325mg three times daily. Patients will be instructed to take on an empty stomach or with an acidic beverage like orange juice. Patients will continue oral iron supplementation through delivery, then refer to their treating physician for further postpartum consumption. Patients will be asked to report any side effects of oral iron between 2 4 weeks after randomization. Side effects will also be assessed at delivery along with reported compliance to the oral iron regimen.
- 2. Intravenous Iron- The intravenous iron infusion will occur in the form of 975mg of intravenous iron dextran diluted in 250 or 500mL of 0.9% sodium chloride given as a single dose over 1-2 hours. Prior to starting the treatment dose, participants will receive a test dose of 0.5mL (25mg) of iron dextran and will be monitored by hospital nursing staff for 20-30 minutes (or per local infusion protocol) to ensure there are no transfusion IVIDA.Version [6.2] 09.18.2019

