- Other major deficiencies in informed consent or HIPAA authorization process or documentation (e.g., substantive outdated informed consent or HIPAA content, such as missing study procedures information, that may affect subjects' willingness to participate).

Study Conduct Events Reportable at IRB Renewal:

Events that do not meet the criteria for prompt reporting should be reported at the time of next study renewal to ensure the IRB has a full understanding of the conduct of the research. **Events that must be reported with the next study renewal submission include:**

- Protocol deviations/protocol noncompliance not previously reported to the IRB.
- Minor noncompliance (i.e., likely not serious or continuing), such as:
 - Use of a consent form that is not the most recently-approved version when the content is not substantively different from the current IRB approved consent.
 - Use of an unstamped consent form when the content is the same as the current IRB approved version.
 - Enrolling more subjects than approved by the IU IRB.
 - Conduct of research by individuals not listed on the study protocol but who have completed appropriate investigator requirements.
 - o Implementing minor wording changes to IRB study documents without prior IRB approval.
 - Failure to appropriately document consent and/or authorization, if the missing information can be clearly corroborated by other documentation (e.g., research notes).

Data Monitoring and Quality Control

Periodic monitoring visits will be made at the investigational site throughout the clinical study to ensure that the investigator obligations are fulfilled, and all applicable regulations and guidelines are being followed. These visits will ensure that the facilities remain acceptable, the investigational plan is being followed, the IRB and local authorities have been notified of approved investigational plan changes as required, complete records are being maintained, appropriate and timely reports have been made to the sponsor and/or its designees and the IRB, and the investigator is carrying out all agreed upon activities.

An annual report will be generated beginning one year after the first enrollment and will include the following:

- A list and summary of adverse events;
- Whether adverse event rates are consistent with pre-study assumptions;
- A summary of recruitment and retention and reason for dropouts;
- Whether the study is on track to be completed and accomplish the stated aims.

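### Infusion reactions get a between-arm test and point estimates but no confidence interval or upper limit, so the plan never states what IV-arm reaction rate the trial can exclude

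*Combined protocol and SAP*

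**What the plan says.** The Synopsis gives the objective as "To assess the effectiveness and safety of treating iron-deficiency anemia in pregnant women with intravenous iron compared to oral iron", and the Objective section repeats the pairing: "This study aims to assess the effectiveness and safety of treating pregnant women with iron-deficiency anemia". Under Study outcomes, safety is the first secondary outcome. It is split into mild/moderate and major infusion reactions, the latter defined as "anaphylaxis-like reaction, seizures, or non-reassuring fetal heart rate tracing".

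Allocation is "randomly assigned in a 1:1 ratio using a computer-generated randomization sequence". Under Randomization and Treatment Groups, only the intravenous arm is assigned an infusion.

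The Data analysis paragraph does not mention infusion reactions. They fall under its general sentence on categorical outcomes: "Categorical variables will be compared using the t or Fisher's exact test, as appropriate". The sentence after it adds risk estimates and risk differences, and analysis is by randomized group. No confidence interval, upper limit, margin or tolerable reaction rate is given.

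The sample size rests on the primary outcome alone: "We estimate that 108 patients will provide 80% power to detect a 60% or greater relative difference in anemia". That number is raised to 120 for 10% loss. No power or precision is stated for safety.

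**The concern.** A between-arm test suits an outcome that both arms can have. An infusion reaction in a trial where one arm has no infusion is different: the oral count should be at or near zero, and the comparison is then a weak way of asking how often the infusion causes harm. With about 60 women per arm and rare events, the test will usually be non-significant even if the true IV-arm rate is several per cent.

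Point estimates do not close the gap. The likeliest result for a rare reaction is zero or very few events. Zero events gives an estimated risk of 0% and nothing to show how far above zero the true rate could be. The same data with an exact limit would say what has been ruled out, which is what a reader deciding on wider use of intravenous iron needs.

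**Working it through.** **Inputs from the protocol.** Total of 120 ("Sample Size: 120 subjects over an estimated 15 - 18 months"), allocated 1:1, so 60 per arm; 108 evaluable, so 54 per arm. Alpha of 0.05, two-sided, is stated for the primary outcome and carried over to safety here.

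**Assumptions.** The documents give no numeric reaction rate; the Potential Risks list uses only frequency words and calls the major events rare. I assume a 5% IV-arm rate as a worked case and show others, and zero oral-arm events. Fisher's test is named in the plan and is the usual choice here, with about 3 events expected in total, or 1.5 per arm. The other test in that sentence is not legible in the text I have; I take it to be chi-square and show both.

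**1. The plan's own figure.** Unpooled two-proportion formula:

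n = (1.960 + 0.842)² × [0.385 × 0.615 + 0.154 × 0.846] / (0.385 − 0.154)² = 7.849 × 0.3671 / 0.05336 = 53.99

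This gives 54 per arm, 108 in total, and 108 / 0.9 = 120. The figure reproduces and concerns anemia only.

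**2. Events needed for significance.** With k events among n IV-arm women and none among n oral-arm women, the two-sided Fisher p-value is 2 × C(n,k) / C(2n,k). For n = 60:

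| k | 3 | 4 | 5 | 6 |
|---|---|---|---|---|
| Fisher p | 0.244 | 0.119 | 0.057 | 0.027 |
| Uncorrected chi-square p | 0.079 | 0.042 | 0.022 | 0.012 |

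Fisher needs 6 events (10% of 60) and uncorrected chi-square needs 4. The thresholds are the same at n = 54.

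**3. Chance of a non-significant result.** This is P(X ≤ 5) for Fisher and P(X ≤ 3) for chi-square, with X ~ Binomial(n, 0.05):

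| Test | n = 60 | n = 54 |
|---|---|---|
| Fisher | 92.1% | 94.8% |
| Chi-square, uncorrected | 64.7% | 71.6% |

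Yates-corrected chi-square matches Fisher. For other true rates with Fisher and n = 60, the chance is 99.1% at 3% and 43.7% at 10% (54.3% at 10% with n = 54). Power of 80% at 60 per arm requires an IV-arm rate of about 13%. If the oral arm had a 1% rate, Fisher power against 5% falls from 7.9% to 4.6% at n = 60.

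**4. Chance of seeing at least one event at a true 5%.** 1 − 0.95⁶⁰ = 95.4%; 1 − 0.95⁵⁴ = 93.7%.

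**5. What an exact limit would say.** For zero events the Clopper-Pearson upper limit is 1 − a^(1/n), with a = 0.05 (one-sided 95%) or 0.025 (two-sided 95%):

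| Result | One-sided 95% upper limit | Two-sided 95% upper limit |
|---|---|---|
| 0/60 | 4.9% | 6.0% |
| 0/54 | 5.4% | 6.6% |

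With events, the two-sided 95% interval is 1.0% to 13.9% for 3/60 and 2.8% to 18.4% for 5/60. The last result (8.3% observed) would be non-significant by Fisher's test.

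**The case against.** The strongest reply is that the plan does estimate: risk estimates and differences follow directly after the test. It also has case-level safety reporting. Serious events go to the IRB and lead site within 24 hours, non-serious events of special interest go to the lead site within 5 days, relationship and severity are assessed, and events are summarized yearly. All of this stands, and it narrows the point to the missing interval or limit. Likewise, the Data analysis paragraph names no interval for any outcome, and anyone can compute an exact limit from reported counts, so nothing is lost for good.

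Three stronger readings are tempting and the documents do not support them.

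- A reader might infer that the plan treats p > 0.05 as proof of safety. No section says so, and no safety decision rule is stated.
- A reader might infer that the trial would fail to notice a 5% reaction rate. It would fail only to reach significance; at least one event would very probably be seen and reported.
- A reader might take the annual-report item "Whether adverse event rates are consistent with pre-study assumptions" as the trial's safety conclusion. It is one line of a monitoring report. The missing reference rate is a gap in detail, and a figure may exist in IRB materials outside these documents.

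It is also fair to say that the between-arm comparison has value for mild/moderate reactions. Nausea, vomiting and diarrhea are listed as risks of both treatments, and oral-arm side effects are collected. Replacing the comparison there would discard useful data.

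**Conclusion.** The point holds as a gap in analysis method. Safety is a stated objective, the oral arm has no infusion, and the plan offers a between-arm test and point estimates without any statement of uncertainty about the reaction rate.

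Under Fisher's test with no oral-arm events, a true 5% major-reaction rate would be non-significant in about 92% of trials with 60 per arm and 95% with 54; with uncorrected chi-square the figures are about 65% and 72%. These rest on the assumed 5% and 0% rates and on carrying over the two-sided 0.05 level. The exact limits need none of those assumptions, only the count and the number infused, which may differ from 54 or 60.

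The deficiency is in what rate the trial can exclude, not in the detection or reporting of individual reactions. It affects a secondary outcome and leaves the primary analysis untouched, but it should be corrected because the remedy is nearly free.

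**What to change.** In Data analysis, add the following.

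- Major infusion reactions: report the number and proportion among women who received an infusion, with an exact (Clopper-Pearson) upper limit, stating in advance whether it is one-sided or two-sided 95%. The infused denominator matters because, under the intention-to-treat rule, women assigned to the IV arm but never infused would dilute the rate.
- Mild/moderate reactions: keep the between-arm comparison and add exact intervals.
- State that a non-significant between-arm test will not be read as evidence of safety.

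Beside the sample size, state that zero major reactions in 60 infused women would exclude only rates above about 5% (one-sided limit 4.9%, two-sided 6.0%; 5.4% and 6.6% with 54).

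The cost is a few sentences and a line of code, with no added patients, visits or data. The downside is a less favourable safety statement: even with no major reactions, the report must say that a rate of up to about 5% has not been excluded.
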